Recording apparatus: A 16-sensor Trigno Wireless data acquisition system (Delsys Inc., Natick, MA) designed for detecting sEMG and IMU signals from single hybrid wireless sensors (*TrignoIM* sensors) will be used for the gait recording sessions. *TrignoIM* sensors will be located on the body during these experiments to record sEMG and IMU signals as described in the Sensor Locations section below. Passive reflector markers will be located on anatomical bony landmarks for motion capture that will be used to validate sensor-based recordings. Sensor signals from *TrignoIM* sensors will be sampled at 2000 samples/sec using EMGWorks software (Delsys Inc., Natick, MA), and interfaced over USB to a PC workstation for post processing. Recordings from motion capture data will be triggered from the EMGworks software so that biomechanical variables can be compared temporally for accuracy. Footswitch sensors or a pair of shoes with pressure pads may be used to record foot pressure while walking.

Sensor locations: The skin area of each sensor location will be prepared using alcohol wipes to cleanse the skin surface and repeated tape peels to remove possible superficial contaminants (oil; dead skin) so as to improve signal quality. We anticipate placement of no more than 16 sensors at any one time on muscle locations such as: gluteus medius, upper-back (trapezius), elbow flexors (biceps brachii), hip flexors (rectus femoris), knee extensors (vastus lateralis), and ankle dorsiflexors/plantarflexors (tibialis anterior and gastroc-soleus) musculature.

Inclusion/Exclusion Criteria

CEREBRAL PALSY

Inclusion criteria:

- Adults or Children (age ≥ 6 y.o.)
- Male or Female
- Confirmed diagnosis of Cerebral Palsy by a neurologist
- CT or MRI imaging consistent with clinical presentation
- Clinical evidence of preserved cognition as determined by the child's neurologist

- Clinical evidence of Mild to Moderate spastic (pyramidal) diplegia as determined by the child's neurologist
- Gross Motor Function Classification System (GMFS) GMFCS Level II ("walks with limitations. Limitations include walking long distances and balancing, but not as able as Level I to run or jump; may require use of mobility devices when first learning to walk, usually prior to age 4; and may rely on wheeled mobility equipment when outside of home for traveling long distances."

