6. Confidentiality risk: The file linking subjects' name to codes will be in paper form and will be stored in a locked file cabinet along with signed consent forms. All sensor data will be stored on the lab servers for at least 3 years in a password protected folder regarding this project. Access will only be available to those working on the project. For cases where data are shared between Columbia and Altec, Inc. only de-identified, raw data will be shared. This removes risk that a patient's privacy may be compromised. In case the subject gives explicit permission to take photo and video recordings during the experiment these will be stored in the password protected project folder on the lab servers. All digital data will be identified only by subject codes.

Potential Benefits to the Subjects

There are no anticipated benefits for subjects in this study aside from the potential benefits to the population of individuals with CP in need of improved robotic rehabilitation devices for gait retraining if our results lead to a more effective system.

Alternatives to Participation

This study does not involve medical diagnostics or treatments for which alternatives should be offered.

Data & Statistical Analysis Plan

A series of signal acquisition and processing software will be developed to analyze gait temporal metrics and range-of-motion from wearable sensors. We will validate these metrics by comparing them to those derived using concurrent motion capture data – considered a gold-standard. We will adopt a repeated measures design (student's t-test statistic) which will be corrected for possible errors associated with multiple comparisons.

Testing of pelvic guiding forces and biofeedback is not designed for efficacy, but for preliminary prototype studies and early development of concepts. Mixed-design analysis of variance followed by post-hoc analysis will be used to determine the effect of the TPAD and mobile TPAD on walking.

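### The multiplicity correction sits on the sensor versus motion-capture t-tests, where it makes a biased metric harder to detect, and the plan gives no agreement criterion to decide validity instead

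*Combined protocol and SAP*

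**What the plan says.** The first paragraph of the Data & Statistical Analysis Plan says that software will be developed to "analyze gait temporal metrics and range-of-motion from wearable sensors". It continues: "We will validate these metrics by comparing them to those derived using concurrent motion capture data", with motion capture named as the gold standard. The next sentence, which closes that paragraph, is the only one that names a test there: "We will adopt a repeated measures design (student's t-test statistic) which will be corrected for possible errors associated with multiple comparisons".

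The Recording apparatus paragraph confirms that the two systems record the same walking: "Passive reflector markers will be located on anatomical bony landmarks for motion capture that will be used to validate sensor-based recordings". The data are therefore paired.

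The pelvic-guidance work has its own paragraph and method: "Mixed-design analysis of variance followed by post-hoc analysis will be used to determine the effect of the TPAD and mobile TPAD on walking".

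For the sensor comparison the documents do not name a correction method, an alpha level, the number of metrics, a sample size, an acceptable difference, an agreement statistic, or a rule for calling a metric valid.

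**The concern.** In most test families a significant result is the favourable claim, and correcting for multiplicity guards against claiming too much. A sensor-versus-reference family runs the other way. A significant difference says that the sensor is biased, and a non-significant one is easily taken as reassurance. Lowering the per-test alpha then guards against the less harmful error (calling a sound metric biased) and increases the more harmful one (missing a real bias).

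The first item under Specific Aims is that wearable technology characterises gait effectively and can drive biofeedback. Temporal measures and ranges of motion, from up to 16 sensors, could make a sizeable family. Under a Bonferroni-type rule, adding metrics to that family raises the bar for flagging each one, with no change in the data.

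**Working it through.** **Where the correction belongs.** The validation sentence and the corrected t-test are adjacent in one paragraph. The pelvic-guidance analysis stands in a separate paragraph with analysis of variance and post-hoc tests. No other use of the t-test is named. On position, the correction attaches to sensor versus motion capture. This is an inference, but a well-supported one.

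**Inputs.** The plan states no figure that can be reproduced. All of the following are assumptions: two-sided alpha 0.05; Bonferroni over *m* = 1, 5, 10 or 20 metrics; one paired difference per subject; *n* = 10, 20 or 30; true bias δ = 0.5 or 0.8 SD of the paired differences.

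**Miss rate for one biased metric.** The metric is flagged when |T| exceeds c = t(1 − 0.05/(2m), n − 1). T follows a noncentral t distribution with n − 1 degrees of freedom and noncentrality δ√n. The miss rate is P(|T| ≤ c).

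For n = 20 and δ = 0.5 the noncentrality is 0.5 × √20 = 2.236. With m = 1, c = 2.093 and the miss rate is 0.44. With m = 10, c = 3.174 and the miss rate is 0.79.

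| Bias | n | m = 1 | m = 5 | m = 10 | m = 20 |
|---|---|---|---|---|---|
| 0.5 SD | 10 | 0.71 | 0.90 | 0.94 | 0.96 |
| 0.5 SD | 20 | 0.44 | 0.70 | 0.79 | 0.85 |
| 0.5 SD | 30 | 0.25 | 0.50 | 0.60 | 0.69 |
| 0.8 SD | 10 | 0.38 | 0.69 | 0.79 | 0.86 |
| 0.8 SD | 20 | 0.08 | 0.25 | 0.35 | 0.45 |
| 0.8 SD | 30 | 0.01 | 0.06 | 0.10 | 0.16 |

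**Largest observed mean difference that stays unflagged.** This is c/√n. At n = 20 it is 2.093/4.472 = 0.47 SD uncorrected and 3.174/4.472 = 0.71 SD with 10 metrics.

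**Other correction methods** (simulation, n = 20, 10 metrics, bias 0.5 SD). When all 10 metrics are biased, Holm gives a miss rate of about 0.72 to 0.75 across correlations from 0 to 0.8, and a false-discovery-rate method gives about 0.56. When only one of the 10 is biased, the false-discovery-rate figure is about 0.78. None of these methods can flag more metrics than uncorrected testing, so the direction is common to all. The size depends on the method and the scenario.

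**What the correction does control.** If every metric is unbiased and the tests are independent, the chance of at least one false flag is 1 − 0.95^10 = 0.40 for 10 metrics and 1 − 0.95^20 = 0.64 for 20. After Bonferroni it is about 0.05.

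**Contrast with an equivalence test** (two one-sided tests at 0.05, n = 20, margins assumed). With a margin of 0.5 SD and a true bias exactly at that margin, a metric wrongly passes 4.6% of the time uncorrected and 0.2% with Bonferroni over 10. Here correction makes passing harder, as it should. The cost is power: with no bias and a margin of 0.8 SD, the pass rate falls from 93% to 52%.

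**The case against.** The strongest objection is that the plan nowhere says a non-significant t-test makes a metric valid. A reader might infer that the plan adopts this rule, but the documents do not state it. It is only the natural reading, because the corrected difference test is the sole criterion offered. A repeated-measures t-test could also cover contrasts between walking conditions, such as holding or not holding the treadmill bars. The paragraph's order makes that less likely without excluding it.

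It can also be said that the correction is a symptom. That stands. With no correction at all, a 0.5 SD bias is still missed 44% of the time at n = 20 and 71% at n = 10. The wrong direction comes from using a difference test to show agreement, and the equivalence contrast confirms this.

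The correction does control a real error, as the 40% chance of a false flag over 10 metrics shows, so it would be wrong to call it pointless. Nor does the text support saying that it would remain a serious flaw whatever else was reported. If agreement statistics decided validity, the corrected t-test would be secondary.

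A reader might also infer that harmful sensor error would be hidden and reach the biofeedback. The bias here is in SDs of the paired differences, and the documents give no such SD. For a precise sensor, 0.5 SD could be trivial in degrees or milliseconds.

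Finally, one could plead early development: "Testing of pelvic guiding forces and biofeedback is not designed for efficacy, but for preliminary prototype studies and early development of concepts". That sentence covers pelvic forces and biofeedback, not sensor validation. It is fair, however, that no efficacy claim depends on this correction.

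**Conclusion.** The point holds in a limited form. As written, the multiplicity correction falls on tests where significance is the unfavourable result. If non-significance is read as support, the correction makes a biased metric less likely to be flagged. That direction held in every scenario tried. The steady growth with each added metric applies to Bonferroni-type rules, and the plan names no method.

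The illustrative rise from 0.44 to 0.79 rests entirely on the assumed alpha, sample size, number of metrics, bias and correction. It shows what could happen and does not estimate what this study will do.

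The correction aggravates a more basic gap, which is that the plan has no criterion for agreement. It should not be concluded that deleting the correction would put the validation right. The change is worth making before analysis because it is cheap and the validation claim depends on it.

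**What to change.** For the sensor versus motion-capture comparison, replace the corrected t-test as the validation criterion:

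- Report each metric's mean sensor-minus-motion-capture difference, its unadjusted 95% confidence interval, and limits of agreement.
- State that a non-significant difference is not evidence of validity.
- If a formal pass/fail claim is wanted, pre-specify an acceptable difference per metric in its own units and require the confidence interval to lie within it. If the claim is that all metrics pass, no multiplicity correction is needed. If separate claims are made per metric, a correction may be applied and then works in the right direction.
- Do not define passing as non-significance on the difference test, corrected or not, whether for single metrics or for all together.
- Keep multiplicity correction for tests where a significant difference is the favourable claim.

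The cost is a few sentences in the plan and no new data, since the paired recordings are already planned. A formal equivalence claim would also require the sample size to be checked against the chosen margins.

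The downside is that validation may look less favourable. Each unbiased metric has about a 5% chance that its interval excludes zero, or about 40% for at least one of 10 independent metrics. An interval that excludes zero should therefore be judged by the size of the bias and not treated as automatic failure.
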